### **9.7. Quality Control**

N/A.

## **9.8. Limitations of the Research Methods**

The missing data that could lead to bias is an identified limitation in this study.

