## 9. RESEARCH METHODS

### 9.1. Study Design

This is a retrospective analysis of approximately 400 patients that were diagnosed with moderate-to-severe plaque psoriasis with difficult to treat sites. Patients will receive Enbrel as treatment for their disease and will include primary and secondary endpoints.

**Primary objective:** Efficacy of Enbrel in Moderate-to-Severe Plaque Psoriasis with difficult to treat sites by measuring the baselines of BSA, PASI and DLQI and compare it with 6 months after treatment and last visit follow-up during study.

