### **9.4. Study Size**

This study will include approximately 400 patients from the registry that meet the inclusion criteria of having moderate-to-severe PsO with difficult to treat sites at presentation.

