### **9.6. Data Analysis**

Detailed methodology for summary and statistical analyses of data collected in this study will be documented as below.

All covariates will be summarized to get information about frequency distribution and mean, median or standard deviation. Numbers and percentages will be provided for dichotomous and polychotomous variables when performing descriptive analysis of categorical data. Means, medians, standard deviations and interquartile range as appropriate will be provided for continuous variables when performing descriptive analysis of continuous data.

The bivariate analysis will be conducted to determine if there is any association between the outcome and the exposure (the covariates). Unadjusted comparisons of baseline characteristics for 0, 4, and 12 months after treatment and last visit disease activity index against outcome measures will be provided. Appropriate tests will be used based on the distribution of the measure: chi-square test will be used for categorical variables, t-test will be used for continuous variables, and the Kruskall-Wallis test for non-parametric variables; p-values will also be generated.

No regression model will be built for this analysis.

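### The plan names missing data as a possible source of bias, but its unadjusted tests and regression ban leave any such bias neither reduced nor assessed

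*Combined protocol and SAP*

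**What the plan says.** The whole of Section 9.8 (Limitations of the Research Methods) is one sentence: "The missing data that could lead to bias is an identified limitation in this study". It gives no amount, variable, visit or mechanism.

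Section 9.6 (Data Analysis) names three tests: "chi-square test will be used for categorical variables, t-test will be used for continuous variables, and the Kruskall-Wallis test for non-parametric variables". The comparisons are to be unadjusted, and the section closes with "No regression model will be built for this analysis". It promises p-values and mentions no confidence interval.

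The primary objective in Section 9.1 takes baseline BSA, PASI and DLQI and will "compare it with 6 months after treatment and last visit follow-up during study". The secondary objective there splits patients into two groups by adherence to Enbrel and compares the same scores at 6 months and last visit. Section 9.6 uses a different set of times: "Unadjusted comparisons of baseline characteristics for 0, 4, and 12 months after treatment and last visit disease activity index against outcome measures will be provided".

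No section defines an analysis set, a rule for an absent score, an imputation or weighting method, a sensitivity analysis or a tabulation of missing values. Section 9.7 (Quality Control) is marked not applicable.

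**The concern.** The plan identifies a threat and then fixes an analysis with no means of reducing or describing it. Read literally, the regression ban also excludes the usual model-based remedies: mixed models and regression-based imputation or weighting.

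The design makes this a practical matter. The data are existing registry records (Sections 9.3 and 9.5), so the plan cannot schedule assessments to fill gaps. The primary comparison needs a 6-month score. A patient can meet the entry rule of at least 1 year on etanercept and still have no recorded 6-month assessment.

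If patients without that score improved by a different amount from those with it, the mean change among patients with scores is biased for the included population. If poorer adherers are also assessed less regularly, which is plausible but not documented, the adherence groups would lose different fractions of patients and their comparison would be distorted too. Under the present plan a reader of the results could not tell whether any of this had happened.

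**Working it through.** **The plan's own figure.** The only number available is the study size: "This study will include approximately 400 patients from the registry". It has no alpha, power, effect size, SD or missing rate behind it, so it cannot be reproduced. It is used below only as the starting number of patients.

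**Inputs**
- N = 400 (Section 9.4).
- Missing fraction m = 10-30%: assumed.
- Shortfall d = 3-6 PASI points, the mean improvement in patients with a score minus that in patients without one: assumed.
- SD of PASI change = 6-10: assumed.

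**Formulas.** The mean change over all patients is (1 - m) × observed mean + m × missing mean. The observed mean therefore differs from it by

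bias = m × d.

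The 95% half-width must use the patients who remain:

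half-width = 1.96 × SD / √(400 × (1 - m)).

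| m | patients left | bias, d = 3 | bias, d = 6 | half-width, SD 6 | half-width, SD 10 |
|---|---|---|---|---|---|
| 10% | 360 | 0.3 | 0.6 | 0.62 | 1.03 |
| 20% | 320 | 0.6 | 1.2 | 0.66 | 1.10 |
| 30% | 280 | 0.9 | 1.8 | 0.70 | 1.17 |

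For example, 0.30 × 6 = 1.8, and 1.96 × 10 / √280 = 1.17.

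- At 10% missing, the bias (0.3-0.6) is below the half-width (0.62-1.03) throughout.
- At 30% missing with SD 6, it exceeds the half-width at both values of d (0.9 and 1.8 against 0.70).
- At 30% missing with SD 10, it exceeds the half-width only when d is above 1.17 / 0.30 = 3.9 points.

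**Scale-free check.** With d in SD units, SE = 1/√(400(1 - m)), and the actual coverage of a nominal 95% interval follows from the normal distribution.

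| m | d (SD) | bias (SD) | bias / SE | coverage |
|---|---|---|---|---|
| any | 0 | 0 | 0 | 95.0% |
| 10% | 0.5 | 0.05 | 0.95 | 84.2% |
| 20% | 0.2 | 0.04 | 0.72 | 89.0% |
| 20% | 0.5 | 0.10 | 1.79 | 56.8% |
| 30% | 0.5 | 0.15 | 2.51 | 29.1% |

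The two tables agree. With SD 6, d = 3 is 0.5 SD, and at 30% missing 0.9 / (6/√280) = 2.51. The first row is the benign case, in which missingness is unrelated to response and there is no bias at any m. The documents give nothing with which to choose between the rows.

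**The case against.** Several readings of these sections are tempting but go further than the text.

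- **That the plan specifies an available-case analysis, with different patients at each time point.** It does not. Section 9.6 says only "t-test will be used for continuous variables" and is silent on which records enter and whether the test is paired. A paired baseline-to-6-month test would use the same patients on both sides. Dropping patients without a score is the likely default, not a stated rule.
- **That the plan predicts a bias which will inflate the primary result.** Section 9.8 says only that bias could arise. Direction is open, because patients who are doing well can also skip visits.
- **That poor responders who stopped early are the missing patients.** Sections 9.2.1 and 9.2.2 exclude anyone with less than 1 year on etanercept. Those patients are outside the study, which is selection and not missing data.
- **That both primary time points are equally exposed.** Last visit is each patient's own last record, so unequal follow-up is the likelier problem there.
- **That the regression ban is the whole defect.** Missing counts, a comparison of patients with and without a 6-month score, and substitution of a single value all need no regression. The plan could have included them and did not.

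A further fair point is that a mixed model assumes missingness depends on observed data. If unrecorded poor response drives absence, the model will not remove the bias.

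These points limit the claim without answering it. Sections 9.6 to 9.8 still contain no rule, no count and no sensitivity analysis for a problem that the plan itself raises.

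**Conclusion.** The concern holds in a limited form. The plan acknowledges possible bias from missing data, restricts itself to three unadjusted tests, rules out regression and provides nothing to reduce, count or bound the effect. This bears mainly on the 6-month comparison and on the adherence-group comparison in Section 9.1.

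The size and direction are unknown. The bias is nil if missingness is unrelated to response. Under the assumed ranges it runs from 0.3 to 1.8 PASI points against half-widths of 0.62 to 1.17, so it can exceed sampling error when missingness is heavy but does not at 10%. None of the missing fractions, shortfalls or SDs comes from the documents. They also do not support saying that bias is present, or that it favours the treatment. What they support is that, if the plan is followed as written, nobody could tell. The plan should be changed, but this does not show that the result is wrong.

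**What to change.** 1. **Reconcile the visit schedule first.** Section 9.6 lists 0, 4 and 12 months, while Sections 8 and 9.1 use 6 months. Until these agree, the visits in any model cannot be fixed.
2. **Replace the regression ban in Section 9.6.** Analyse BSA, PASI and DLQI with a linear mixed model for repeated measures using every recorded scheduled visit. Enter baseline as one of the outcome visits and not also as a covariate. For the adherence comparison, add adherence group and its interaction with visit.
3. **Analyse last visit separately** as paired change from baseline, and report follow-up time.
4. **Describe the missingness.** Report the number of patients with data by variable and visit, and compare baseline scores of patients with and without a 6-month score.
5. **Add one sensitivity analysis** that sets a missing 6-month score to the patient's baseline value. This assumes no improvement, so it is a conservative bound on mean change and not a best estimate.
6. **Extend Section 9.8** to list selection by the 1-year entry rule (Sections 9.2.1 and 9.2.2) as a separate limitation, since no missing-data method applied to included patients repairs it.

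The cost is revised wording and a few hours of analysis on existing data. The estimate may become less favourable. Section 6 gives the end of data collection as 01 August 2020, so the model must be labelled as added after data collection, and its assumption that missingness depends on observed data must be stated.

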## **10. OTHER ASPECTS**

Not applicable.

## **11. PROTECTION OF HUMAN SUBJECTS**

### **11.1. Patient Information**

This study involves data that exist in anonymized structured format and contain no patient personal information.

### **11.2. Patient Consent**

As this study involves anonymized structured data, which according to applicable legal requirements do not contain data subject to privacy laws, obtaining informed consent from patients by Pfizer is not required.

### **11.3. Institutional Review Board (IRB)/Independent Ethics Committee (IEC)**

There must be prospective approval of the study protocol, protocol amendments, and other relevant documents (eg, informed consent forms if applicable) from the relevant IRBs/IECs. All correspondence with the IRB/IEC must be retained. Copies of IRB/IEC approvals must be forwarded to Pfizer.

### **11.4. Ethical Conduct of the Study**

The study conducted in accordance with legal and regulatory requirements, as well as with scientific purpose, value and rigor and follow generally accepted research practices described in Guidelines for Good Pharmacoepidemiology Practices (GPP) issued by the International Society for Pharmacoepidemiology (ISPE), Good Epidemiological Practice (GEP) guidelines issued by the International Epidemiological Association (IEA), and Good Practices for Outcomes Research issued by the International Society for Pharmacoconomics and Outcomes Research (ISPOR).

## **12. MANAGEMENT AND REPORTING OF ADVERSE EVENTS/ADVERSE REACTIONS**

[figure not shown]
This study involves data that exist as structured data by the time of study start.

In these data sources, individual patient data are not retrieved or validated, and it is not possible to link (ie, identify a potential association between) a particular product and medical event for any individual. Thus, the minimum criteria for reporting an adverse event (AE) (ie, identifiable patient, identifiable reporter, a suspect product, and event) cannot be met.

## **13. PLANS FOR DISSEMINATING AND COMMUNICATING STUDY RESULTS**

In the event of any prohibition or restriction imposed (eg, clinical hold) by an applicable competent authority in any area of the world, or if the investigator is aware of any new information which might influence the evaluation of the benefits and risks of a Pfizer product, Pfizer should be informed immediately.

[figure not shown]
PFIZER CONFIDENTIAL

## 15. LIST OF TABLES

None.

[figure not shown]
[figure not shown]
## 16. LIST OF FIGURES

None.

## ANNEX 1. LIST OF STAND-ALONE DOCUMENTS

Number	Document reference number	Date	Title
1	Section 4	15 June 2021	The Impact of Difficult to Treat Sites on Biological Treatment Response in Patients with Moderate-to-Severe Plaque Psoriasis

PFIZER CONFIDENTIAL

